### 5.3 SAFETY-RELATED STATISTICAL QUANTITIES

Safety assessment are performed based on the safety data collected directly from the eCRF or lab report.

## **6. STATISTICAL DESIGN AND ANALYSIS**

### **6.1 STUDY POPULATION**

#### **6.1.1 Evaluable Subjects and Per Protocol Population (PPP)**

##### **PPP-PK: Per-Protocol Population for PK Analysis**

The PPP-PK is defined as all subjects who have received both study drugs during the study and are evaluable for both treatments. Primary PK analyses will be performed based on the PPP-PK.

In order to be evaluable for the primary analyses of this study, a subject must meet all of the following six (6) criteria for both treatments:

- (1) Correct dose and administration for both T and R treatments.
- (2) Nineteen (19) or more of 25 post-dose PK data (>75%) for serum concentration points are available;
- (3) There are no more than four (4) consecutive missing PK data points;
- (4) The baseline PK data point and the 12-hour post-dose PK data are available;
- (5) At least five (5) of the seven (7) PK data points at 50, 55, 60, 65, 70, 75, and 80, post-dose are available;
- (6) At least three (3) of the PK data points at 5, 6, 8, and 10 hours post-dose are available.

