Isolated serum will be distributed into two (2) 2.0 mL cryo vials, approximately 1.5 mL in the first aliquot and the remainder in the second aliquot. The serum samples will be frozen on dry ice and then immediately (within 60 minutes following serum isolation) stored in a freezer at -20°C or lower until analysis.

PK Sampling Schedules and Time Window

PK sampling: a total of twenty-eight (28) blood samples for each study visit will be collected. The blood sampling schedule and allowed time window during each study visit are listed in **Table B**.

Sample ID

The sample ID for PK samples (before centrifugation) is defined as

“I4-B-*nn*-V-XX:”

where, *I4-B-*nn** is the subject ID; *V* is the study visit code, V=1 or 2; and *XX* is the two-digit time-

point sequential number of the sample: 01, 02, 03, ...28 insulin as listed in **Table B**.

Table B PK Blood Sampling Schedule (6 mL per sample)

Seq. #	Scheduling	Time window	Sample No., "XX"	#	Scheduling	Time window	Sample No., "XX"
1	-60 min	± 5 min	01	15	75 min	±3 min	15
2	-30 min		02	16	80 min	±5 min	16
3	0 min	±1 min	03	17	90 min		17
4	5 min		04	18	105 min		18
5	10 min		05	19	120 min		19
6	20 min	±2 min	06	20	150 min		20
7	25 min		07	21	180 min	±10 min	21
8	30 min	08	22	210 min	22		
9	40 min	±3 min	09	23	4 h	±10 min	23
10	50 min		10	24	5 h		24
11	55 min		11	25	6 h		25
12	60 min		12	26	8 h	±20 min	26
13	65 min		13	27	10 h		27
14	70 min	14	28	12 h	28		
Total							28 (168mL)

The sample ID for PK samples (after centrifugation) is defined as

"I4-B-nn-V-XX-k"

where *k* is the aliquot number (A or B). The sample ID labels will be printed in blue colored fonts with label size for the tube is 1/2"×1¾" (Avery label 5667), as demonstrated below:

I4-B-nn-V-XX-k

Sample Transportation and Analysis

Prior to sample transportation, all samples should be stored in a box and must be organized in sequential order by subject and separated by aliquot. The chain of custody, temperature control and related documents for sample transportation must be recorded. During transportation of PK samples from the site to Amphastar, the temperature should be below -20°C. The transportation between the study site and the test laboratory must be completed within 48 hrs. The chain of custody, elapsed time for transport, temperature control and related documents for sample transfer must be recorded and documented. All serum samples will be stored at -50 °C or lower in the

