4.3 Rationale for Study Design and Endpoints

A single dose cross-over design is chosen in order to allow each subject to act as his/her own control in order to reduce variability.

A minimum 7-day wash-out period before and between the two treatment periods is introduced to ensure a sufficient wash-out from previous dosing, in order to avoid any carry-over effects.

Randomization is used to avoid bias introduced through an association between trial drug allocation order and subject characteristics.

Blinding of participants and personnel is introduced in order to avoid performance bias.

Due to the variability in fasting blood glucose concentrations in subjects with type 1 diabetes, which might affect the metabolic response to the study drug, healthy subjects have been chosen. A study in healthy subjects is likely to produce less PK variability compared with that in patients with potentially confounding factors such as underlying and/or concomitant disease and concomitant medications. C-peptide and endogenous human insulin in parallel to the insulin aspart concentration is measured during the study, to detect potential changes in endogenous insulin secretion and enable a correction for endogenous insulin secretion, if necessary.

Enrollment criteria will favor a generally insulin-sensitive population and diseases/conditions and medications associated with insulin resistance have been excluded.

The sample size of 60 subjects is chosen as it represents a typical number for a biosimilar study. The use of the euglycemic glucose clamp method is chosen to assess PD in a standardized fashion and for safety reasons to avoid hypoglycemia.

Glucose levels below approximately 60 mg/dL must be avoided because they result in the

stimulation of counter regulatory hormones (epinephrine, glucagon, cortisol, growth hormone) to increase blood glucose concentrations and lead to a rapid and pronounced worsening of insulin sensitivity, thus influencing the estimated time-action profile of the investigated insulin preparation. Therefore, blood glucose (BG) inclusion criterion prior to the clamp is limited to a fasting plasma glucose value ≥ 75 mg/dL (for the mean of the $-30 \leq$ to -10 min glucose measurements), as the target clamp level is 5 mg/dL below the mean fasting BG values. The chosen target level of mean fasting glucose minus 5 mg/dL will ensure that endogenous insulin secretion is sufficiently suppressed and will not interfere with PK and PD assessments.

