7.15 Pharmacokinetic Assessments and Schedule

Blood for PK analysis of the IP, the human insulin analog, will be collected at the time points indicated in the SOE ([Appendix A](#)) and follow the PK blood sampling schedule below.

At each sampling time point, 1.0 mL of blood will be discarded for waste (utilizing a throw away tube). Thereafter, one 6.0 mL whole blood sample per scheduled time point will be collected to provide a minimum of 1.5 mL of serum for PK measurements and 1.5 mL of serum as a secondary back-up sample. Instructions for sample processing and shipment are provided below.

Table 7-2 PK Blood Sampling Schedule (6 mL per sample)

Seq. #	Scheduling	Time window	Sample No., "XX"	#	Scheduling	Time window	Sample No., "XX"
1	-60 min	± 5 min	01	15	75 min	±3 min	15
2	-30 min		02	16	80 min	±5 min	16
3	0 min	±1 min	03	17	90 min		17
4	5 min		04	18	105 min		18
5	10 min	±2 min	05	19	120 min		19
6	20 min		06	20	150 min	±10 min	20
7	25 min	±3 min	07	21	180 min		21
8	30 min		08	22	210 min		22
9	40 min		09	23	4 h		23
10	50 min	±3 min	10	24	5 h	±20 min	24
11	55 min		11	25	6 h		25
12	60 min		12	26	8 h		26
13	65 min		13	27	10 h		27
14	70 min		14	28	12 h		28
Total							28 (168mL)

PK Sample Processing and Shipment Instructions are described below:

(1) Sampling Procedure

A catheter will be inserted into one of the antecubital region veins for blood sampling. Alternatively, collection from a vein from the hand or forearm for easier access or via venipuncture is also acceptable. PK blood draws should use the opposite arm of the glucose infusion/clamp. Preferably, the arm with better venous access will be used for PK samplings, and the opposite arm for the glucose infusion/clamp. In case of extraordinary situations, such as IV infiltration etc, the PK samples could be collected from the arm of the clamp, for safety reason.

After each blood sample collection, a catheter flush will be performed to avoid catheter clot formation and prevent interference between samples.

At each PK sampling point, the first 1 mL of blood will be discarded for waste (utilizing a disposable tube), and blood samples (~6 mL per sample), will be collected in a serum separation tube and left to stand at room temperature for 30 - 60 minutes. Each sample will be centrifuged at 2-8°C, 1,000-1,300 g for 20 minutes.

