### 2.4.2 Pharmacokinetic (PK) Endpoints for Human Insulin (HI)

#### (1) Primary PK Endpoints for HI

- (i)  $C_{HI_{max}}$ , defined as the maximum serum HI concentration;
- (ii)  $AUC_{HI(0-12h)}$ , defined as area under the curve (AUC) of HI concentrations for time 0 to 12 hours; and

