## 5. CALCULATION OF RELATED STATISTICAL QUANTITIES

### 5.1 PK PARAMETERS

#### 5.1.1 Primary Endpoints and Related Quantities

- (1)  $C_{max}$ , in units of pg/mL, is defined as the maximum of observed serum Insulin Aspart (IA) concentration for a given subject and given treatment over all PK sample concentrations:

$$C_{max} = \max(C_1, \dots, C_i, \dots, C_n) \quad i = 1, 2, 3 \dots n \quad (13)$$

where  $n=26$ , and  $C_i$  is rounded to 10% of the quantitative limit (QL) of the validated test method for IA.

- (2)  $AUC_{IA(0-12h)}$ , in units of pg/mL\*hr, can be calculated per the trapezoidal rule and sampling time for each treatment of each subject as given the Eq. (14):

$$AUC_{0-12h} = \sum_{i=1}^{n-1} \frac{C_i + C_{i+1}}{2} (t_{i+1} - t_i) \quad (14)$$

where  $n$  is the number of available PK measurements,

$t_1$  is the baseline, and

$t_n$  is the sampling time for the last scheduled PK measurement,  $t_n = 12 \text{ hours}$ .

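### The SAP accepts only the 0-min sample as PK baseline, gives it no fallback, and its sampling window differs between tables, so a subject can leave the primary PK set over a value that carries almost no information

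*SAP*

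**What the plan says.** Protocol synopsis section IV states that "a total of twenty-eight (28) blood samples for each study visit will be collected". Table B there, Protocol Table 7-2 and SAP Table 3 all list -60, -30 and 0 min, followed by 25 post-dose times.

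The SAP counts from 0 min. Section 4.2 sets t1 = 0, and Table 4 lists C1 at 0 min. Section 5.1.1 takes Cmax over n = 26 points and says of t1, the first point in the AUC sum, that it "is the baseline, and". Section 5.1.2(3) equates C1 with baseline. No rule uses the -60 or -30 min results.

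For PPP-PK, SAP 6.1.1 says "a subject must meet all of the following six (6) criteria for both treatments". Criterion (4) reads "The baseline PK data point and the 12-hour post-dose PK data are available". Section 6.2.2 takes non-evaluable subjects out of the primary and secondary analyses. Section 6.2.1 offers interpolation only to subjects already evaluable, and the one endpoint of the curve that it rescues is the 12-hour sample. Section 6.3.2 treats samples excluded for severe deviation as missing, and section 6.3.3 makes the dataset with those exclusions the formal PK result.

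The window for the 0-min sample is ±1 min in Protocol Tables B and 7-2 and SAP Table 3, and -5 to 0 min in Protocol Appendix B. SAP Table 4 gives C1 no window and no flag limit.

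**The concern.** A per-protocol rule should remove subjects whose data cannot support the endpoint. A missing 0-min aspart value does not meet that description. The expected value is about zero, and two other pre-dose samples from the same morning are available to confirm it. As written, the rule discards a full pair of profiles for the lack of one redundant number.

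The conflicting windows make this worse. Staff who follow Appendix B can draw a sample that the SAP's own formula would call a severe deviation. Because Table 4 leaves C1 blank, the outcome falls to a case-by-case decision of the Management Review Board. In the other direction, ±1 min allows a baseline drawn after the injection. In a pivotal equivalence analysis based on a per-protocol set, membership should not depend on which table was followed.

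**Working it through.** **1. Reproduce the schedule.** 28 samples x 6 mL = 168 mL, as printed. 28 = 3 at or before 0 min + 25 post-dose. The SAP's n = 26 is the 0-min sample plus the 25 post-dose samples, so two pre-dose samples per visit go unused. SAP 6.1.1 never says in words that baseline means 0 min, but t1 = 0, C1 = baseline and n = 26 leave no other reading.

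**2. What the 0-min aspart value contributes.**
- Trapezoid weight of C1 in AUC(0-12h): (5 - 0)/2 = 2.5 min of 720 min, or 0.35%.
- Carry-over: the minimum washout is 7 x 24 x 60 = 10,080 min. At the 81-min half-life cited in Protocol 4.2 this is 10,080/81 = 124 half-lives.

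**3. Subjects removed.** The documents give no missed-draw rate, so p per draw is an assumption, with draws taken as independent. A subject needs the value at both visits, so the probability of removal is 1 - (1 - p)^2. If any of the three pre-dose draws may serve, it is 1 - (1 - p^3)^2.

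| p | Probability as written | Of 60, as written | Of 60, with fallback |
|---|---|---|---|
| 0.5% | 1.0% | 0.6 | 0.00001 |
| 1% | 2.0% | 1.2 | 0.0001 |
| 2% | 4.0% | 2.4 | 0.001 |
| 5% | 9.8% | 5.9 | 0.015 |

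Missed draws within one visit may be correlated, for example through a failed catheter. The fallback would then rescue fewer subjects than the last column shows.

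**4. Power, if losses were not replaced.** Protocol 10.3 shows no CV, ratio or power, so this is illustration only (two one-sided 5% tests, assumed true ratio 0.95). Going from 60 to 57 subjects lowers power from 93.6% to 92.5% at a within-subject CV of 30%, and from 76.6% to 74.3% at a CV of 40%.

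**5. Windows.** The intervals -1 to +1 min and -5 to 0 min overlap only from -1 to 0 min. SAP Eqs. (3) and (4) are F = max(g/2 - w, 0) and H = min(F, 2w). With w = 1 min:
- Before dosing: H cannot exceed 2 min whatever neighbour is used, so the furthest draw that is merely flagged is at -(1 + 2) = -3 min. A draw at -4 min meets Appendix B but lies beyond this limit. SAP 4.2 then makes it a severe deviation, and SAP 6.3.2 allows its exclusion as missing, which fails criterion (4).
- After dosing: g = 5, F = 2.5 - 1 = 1.5 and H = 1.5. A draw up to 1 + 1.5 = 2.5 min after the injection would be flagged but not severe.

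Table 4 prints none of these limits for C1, so they are what the formulas imply, not what the SAP states.

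**The case against.** The strongest reply is that the cost is minor. Requiring a baseline in a per-protocol set is conservative. A removed subject stays in the treated population, which has a supportive PK analysis (SAP 6.1.2). The PPP-PD criteria need no PK baseline. The protocol enrols until 60 subjects are evaluable, so the loss is at most a few extra enrolments unless it is discovered late. The SAP also analyses the data with severe deviations included. Because Table 4 gives C1 no limit, a draw at -4 min need not be excluded at all. A draw within a minute of a subcutaneous injection should barely change aspart. All of this stands, and it limits the size of the point. It does not justify having no fallback, or settle which window governs.

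A reader might go further and infer that the human-insulin maximum ("defined as the maximum serum HI concentration") is largely the pre-dose level, so that the objective on endogenous insulin goes unaddressed. The documents do not support either step.
- Eq. (13) is written for aspart only, and no human-insulin levels or amount of suppression are given. Protocol 4.3 says only that the clamp target "will ensure that endogenous insulin secretion is sufficiently suppressed".
- In a simulation over the 26 points (assumed noise CV 10 to 30%, suppression developing from 10 to 60 min), the maximum fell on the 0-min sample in at most about 31% of profiles, even with 50% suppression. It fell somewhere in 0 to 10 min in 28 to 67% of profiles with 20% suppression and 62 to 91% with 50%.
- AUC_HI(0-12h) stands beside the maximum in SAP 2.4.2 and does register suppression. Take sustained suppression of 50% under T and 20% under R, same onset. The areas in baseline-minutes are 10 + 50 x 0.75 + 660 x 0.5 = 377.5 and 10 + 50 x 0.9 + 660 x 0.8 = 583, a ratio of 0.65.
- SAP 5.2.3, Eqs. (29) and (30), adjusts GIR by measured human insulin after dosing and compares T with R.

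**Conclusion.** The point holds for aspart and for the window. The SAP relies on one of three scheduled pre-dose samples. If that value is missing or excluded at either visit, the subject leaves the primary and secondary PK analyses with no fallback. Under the assumed 0.5 to 2% missed draws this affects about 0.6 to 2.4 of 60 subjects, with little effect on power. The 0-min window is inconsistent across the tables, and an Appendix B-compliant draw before -3 min can end as a missing baseline under the SAP's own formulas. The main gain from correcting this is a pre-specified baseline and fewer discretionary exclusions from the set that decides equivalence.

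On human insulin only a narrower remark survives. The plan does not say whether the maximum and its time include pre-dose points, and they may reflect the pre-dose level if secretion is suppressed.

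**What to change.** - In SAP 5.1.1 and 6.1.1, define the aspart baseline as the last available pre-dose value: 0 min, else -30 min, else -60 min. Place it at t = 0 so that the AUC interval is unchanged.
- Let any one of these values satisfy the baseline part of PPP-PK criterion (4).
- Give the 0-min sample one pre-dose-only window in Protocol Tables B and 7-2, Protocol Appendix B and SAP Table 3. Enter the same window and its flag limits for C1 in SAP Table 4.
- Optionally, state in SAP 2.4.2 whether the human-insulin maximum and its time include pre-dose points.

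The cost is SAP wording, one derived variable and a few table cells in both documents. The samples are already scheduled for collection and assay, so no procedure is added. The changes should be made before treatment codes are opened.

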##### **PPP-PD: Per-Protocol Population for PD Analysis**

The PD BE evaluation will be performed based on the PPP-PD. An evaluable subject for PD primary endpoint analyses of this study must meet all of the following four (4) criteria for both treatment arms:

- (1) Correct dose and administration for both T and R treatment;
- (2) More than 90% per minute GIR records are available;
- (3) The clamp precision < 12% for both T and R treatments; and
- (4) The clamp Deviation From Target (DFT) <12% for both T and R treatments.

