7.14.4 Glucose Clamp Quality Parameter

The quality of the clamp data will be reviewed on a regular basis by the PI and the clamp supervisors at regularly scheduled Data Review Meetings. The following parameters are included in the review:

- Clamp coefficient of variation (CV): Coefficient of variation of device BG measurements calculated by the following formula:

$$(\text{SD of Device BG} / \text{Mean Device BG}) * 100$$

- Clamp deviation from the target (DFT): Mean difference (mg/dL) between device and target BG level represented as a percentage, calculated as follows:

$$[\text{Mean (device BG} - \text{target level)} / \text{target level}] * 100$$

- Accuracy: Mean difference of all paired BG measurements of device vs reference method represented as a percentage.

Calculations for CV and DFT will be based on each clamp from the minute that the glucose infusion rate is initiated (Start of GIR) to the minute that the glucose infusion rate is no longer required (End of GIR) or at the end of the clamp at the 12-hour mark, whichever appears first. Note that an End of GIR is not necessarily an end of the clamp.

In case a subject's GIR requirement is intermittent or has interrupted periods during the clamp, the PI will review the clamp data and determine how the clamp quality will be calculated.

Generally, overall mean clamp CV and DFT for the clamps should be less than 10%. If the calculated CV or DFT for an individual clamp is $\geq 12\%$, the clamp data for that clamp should be considered for exclusion from the final data analysis and the clamp should be repeated (if possible), or the subject should be replaced, following discussion between the Investigator and the Sponsor. If the accuracy calculation is $> 12\%$ but the CV and DFT are $< 12\%$, it will be at the discretion of the Principal Investigator to determine if the clamp data quality is acceptable. [REDACTED] Clinical Data Management Team and the Sponsor will also be consulted.

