#### 4.3.2 Deviation from Target (DFT)

The clinical protocol required that “the individual blood glucose clamp target level will be determined for each subject by the mean fasting glucose level minus 5 mg/dL.”, which can be defined as  $g_0$ .

The baseline of blood glucose is the mean fasting glucose level from three (3) results measured by YSI 2300 STAT Glucose Analyzer at -30min, -20min, and -10min.

The actual blood glucose level for each corresponding clamp data point is denoted as  $g_{i,X}(t)$ . The average deviation from the target (DFT) for a given subject  $i$  in treatment  $X$  is then defined as

$$d_{i,X} = \frac{1}{n_t} \sum_t \frac{g_{i,X}(t) - g_0}{g_0} \times 100\% \quad (8)$$

In calculation DFT (Eq. (9)), the time  $t$  runs the same as that for Eq. (5). It is also expected  $d_{i,X} < 12\%$ . For the subjects with  $DFT \geq 10\%$ , the data should be flagged and tabulated. If  $d_{i,X} \geq 12\%$ , the clamp data should be rejected.

The DFT for a treatment  $X$  is obtained by the following calculation:

$$D_X = \frac{1}{n_X} \sum_{i=1}^{n_X} d_{i,X} \quad (9)$$

where  $n_X$  is the number of subjects in the treatment X.

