#### 4.3.3 Accuracy

Accuracy (denoted as  $A$ ) is defined as mean difference of all paired BG measurements of device vs reference method represented as a percentage.

$$A = \frac{1}{n'_t} \sum_t \left( \frac{g_{i,X}(t) - g'_{i,X}(t)}{g'_{i,X}(t)} \times 100\% \right) \quad (10)$$

where  $g^{i,X}$  is the BG measured by Biostator,  
 $g'_{i,X}$  is the BG measured by YSI Glucose analyzer,  
 $t$  is the time point when BG measurement by both methods are available, and  $t$  runs through all such both method data available time points;  
 $n'_t$  is number of time points with BG measurement by both Biostator and YSI Glucose analyzer.

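### The clamp deviation-from-target limit has no lower side, so a steady clamp running well below target stays in the primary PD set by default

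*SAP*

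**What the plan says.** SAP 4.3.2 introduces "The average deviation from the target (DFT) for a given subject" and treatment in Eq. (8): the time average of (g - g0)/g0 in percent. Here g is clamp blood glucose and g0 is the target, which is baseline minus 5 mg/dL. A clamp is flagged at DFT of 10% or more. At 12% or more, "the clamp data should be rejected". Eq. (9) averages the signed subject values to give a treatment-level figure, D_X.

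Protocol 7.14.4 uses the same construction: "Mean difference (mg/dL) between device and target BG level represented as a percentage". Its trigger is also on the upper side only. At 12% or more for CV or DFT, "the clamp data for that clamp should be considered for exclusion from the final data analysis", and the clamp is to be repeated if possible or the subject replaced, after discussion between investigator and sponsor.

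SAP 6.1.1 makes PPP-PD the set for the PD bioequivalence evaluation. Its four criteria, required for both treatments, are:

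1. correct dose and administration;
2. more than 90% of the per-minute glucose infusion rate (GIR) records available;
3. a precision (CV) under 12% in each clamp;
4. "The clamp Deviation From Target (DFT) <12% for both T and R treatments".

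Only the fourth measures distance from target. Precision (SAP 4.3.1, Eq. 6) is the SD of glucose divided by the clamp's own mean.

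**The concern.** A limit on deviation from target should work in both directions. As written, it removes clamps that average too high and has no effect on clamps that average too low, however far.

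The unscreened direction is the one the protocol warns about. Protocol 4.3 says "Glucose levels below approximately 60 mg/dL must be avoided because they result in the" release of counter-regulatory hormones, with a fall in insulin sensitivity that alters the measured time-action profile. In addition, both primary PD endpoints rest on GIR defined as the glucose needed to hold the target level, and GIR recorded while glucose sits well below target is not that quantity.

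The 12% trigger in Protocol 7.14.4 also starts the repeat-or-replace process, so a low clamp does not prompt that either. If sponsor and programmer read deviation differently, one as a magnitude and the other as the signed formula, they could build different PPP-PD sets from the same data.

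**Working it through.** The plan states no figure derived from this rule, so there is none to reproduce. The check applies the rule to constructed clamps.

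**Inputs.**
- DFT = mean of (g - g0)/g0 × 100; pass if below 12% (SAP 4.3.2, PPP-PD criterion 4).
- CV = SD / mean glucose × 100; pass if below 12% (SAP 4.3.1, PPP-PD criterion 3).
- Permitted baseline 75 to 99 mg/dL (Protocol 5.4), so the target lies between 70 and 94 mg/dL.
- Glucose SD within a clamp is not given. It is assumed to be 3 or 5 mg/dL, as stated.
- Dosing is taken as correct, records as complete, and the subject's other clamp as acceptable.

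**Worked example.** Baseline 80, target 75, mean glucose 57, SD 3:
- DFT = (57 - 75)/75 = -24.0%, which is below 12%: passes.
- CV = 3/57 = 5.3%, which is below 12%: passes.
- Mirror image, mean glucose 93: DFT = (93 - 75)/75 = +24.0%: rejected.

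**Range of targets, assumed SD 5 mg/dL.**

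| Target | Mean offset | Mean glucose | DFT | CV | Result as written |
|---|---|---|---|---|---|
| 70 | +12% | 78.4 | +12.0% | 6.4% | rejected |
| 70 | -15% | 59.5 | -15.0% | 8.4% | passes |
| 70 | -20% | 56.0 | -20.0% | 8.9% | passes |
| 70 | -30% | 49.0 | -30.0% | 10.2% | passes (CV flagged) |
| 80 | -20% | 64.0 | -20.0% | 7.8% | passes |
| 80 | -25% | 60.0 | -25.0% | 8.3% | passes |
| 94 | -30% | 65.8 | -30.0% | 7.6% | passes |

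A steady mean of 60 mg/dL corresponds to DFT of (60 - 70)/70 = -14.3%, (60 - 80)/80 = -25.0% and (60 - 94)/94 = -36.2% at targets 70, 80 and 94. The DFT criterion passes all three.

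**With the limit on the absolute value.** Clamps at -12%, -15%, -20%, -25% and -30% are rejected, as those at +12% and +15% already are. Clamps at +11.9% and -11.9% still pass. Mean glucose must then exceed 0.88 × target, which is 61.6, 70.4 and 82.7 mg/dL at targets 70, 80 and 94.

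**Treatment-level summary.** Because Eq. (9) averages signed values, a clamp at +10% and one at -10% contribute (10 - 10)/2 = 0% to D_X, whereas their mean absolute deviation is 10%.

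**The case against.** **Other routes could remove a low clamp.** Protocol 7.14.4 has the principal investigator and clamp supervisors review CV, DFT and accuracy regularly. Protocol 10.1.1 limits the PD population to subjects without major deviations thought to affect PD. SAP 6.3.2 lets the Management Review Board exclude data for severe deviations, and its list is open-ended. This stands in part: a low clamp is not bound to stay in. But these routes are discretionary and none states a low-side limit, so it stays in by default.

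**Very low clamps would be noticed.** In the worked example, if readings are normal, about 37% are at or below 56 mg/dL and about 1% (some 7 of 700) at or below 50. Those are the levels Protocol 8.3.1.1 uses for hypoglycemia, with symptoms required at the higher one. That section governs safety action and event recording; it does not define PD evaluability.

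**Sustained low glucose should be uncommon.** GIR is adjusted minute by minute, the operator can override it, an external glucose line is available, and YSI checks run about every 30 minutes (Protocol 4.2 and 7.14). This is fair. The documents give no frequency, and none can be derived.

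**A reader might infer that swings above and below target cancel within a clamp and so escape.** They do not escape unchecked. When DFT is zero, the clamp mean equals the target and CV is the root-mean-square deviation from target, already limited to below 12%. A clamp half at +11% and half at -11% has DFT 0% and CV about 11%; SAP 4.3.1 flags it at 10%, and it would pass a 12% mean-absolute rule as well. Nor are only high clamps screened out: the CV criterion removes erratic clamps in either direction.

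**A reader might extend the point to accuracy**, which "is defined as mean difference of all paired BG measurements of device vs reference method represented as a percentage". That compares the Biostator with the YSI, not glucose with target. It is not a PPP-PD criterion, and Protocol 7.14.4 leaves values above 12% to the investigator's discretion when CV and DFT are acceptable.

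**Conclusion.** The point holds on the text of both documents. A steady clamp averaging more than 12% below target meets every PPP-PD criterion and remains in the primary PD set unless someone chooses to remove it, while the same deviation above target is rejected. The result for the DFT criterion needs no assumption. The CV values rest on assumed SDs of 3 or 5 mg/dL, and a low clamp with CV of 12% or more would be rejected on precision.

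A reader might go further and conclude that the GIRmax and AUC_GIR comparison is biased. The documents do not support that. They give no frequency of low clamps and no effect on GIR. The same rule also applies to both treatments in a blinded crossover, so no differential effect on the T/R ratio is established. The protocol's stated worry is an absolute level of about 60 mg/dL, which corresponds to quite different percentage deviations at different targets. The grade is should-fix: a one-sided rule in the definition of the primary PD set that is cheap to correct.

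**What to change.** Before the PD analysis set is fixed:

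- In SAP 4.3.2, flag when |d| is 10% or more and reject when |d| is 12% or more, with d as in Eq. (8).
- In PPP-PD criterion (4), require |DFT| below 12% for both treatments.
- In Protocol 7.14.4, state the DFT limits on the absolute value.
- Beside the signed D_X in Eq. (9), report the mean of |d| by treatment. Keep the signed figure, since it shows the direction of any systematic offset.

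The cost is wording in three places and one extra summary. A few more clamps may be flagged or rejected, and under Protocol 7.14.4 some of these may lead to a repeat or a replacement subject. Making the change after PD results are known would be post hoc.

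The change makes the limit symmetric about the target; it does not keep every reading above 60 mg/dL. At target 70 a mean just above 61.6 would still pass. With an assumed SD of 5 and normal readings, about 37% of values would then be below 60, since (60 - 61.6)/5 = -0.32.
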